7.11.1.2 Displays of Treatment-Emergent Adverse Events

Analysis Set: Safety Analysis Set

Analysis

Variable(s) : TEAE

Categories: Intensity [Mild, Moderate, Severe]

Time of Onset (day) [1<= - <=28, 29<= - <=56, 57<= - <=84, 85<= - <=Max]

Analytical

Method(s) : The following summaries will be provided using frequency distribution for each treatment group.

TEAEs will be coded using the MedDRA and will be summarized using SOC and PT.

SOC will be sorted alphabetically and PT will be sorted in decreasing frequency for tables provided by SOC and PT. SOC and PT will be sorted in decreasing frequency for tables provided by System Organ Class only or PT only.

(1) Treatment-Emergent Adverse Events by System Organ Class and

Preferred Term

- (2) Treatment-Emergent Adverse Events by System Organ Class
- (3) Treatment-Emergent Adverse Events by Preferred Term
- (4) Drug-Related Treatment-Emergent Adverse Events by System Organ Class and Preferred Term
- (5) Intensity of Treatment-Emergent Adverse Events by System Organ Class and Preferred Term
- (6) Intensity of Drug-Related Treatment-Emergent Adverse Events by System Organ Class, and Preferred Term
- (7) Treatment-Emergent Adverse Events Leading to Study Drug Discontinuation by System Organ Class and Preferred Term
- (8) Serious Treatment-Emergent Adverse Events by System Organ Class and Preferred Term
- (9) Treatment-Emergent Adverse Events by System Organ Class and Preferred Term Over Time
- (10) Most Frequent Treatment-Emergent Adverse Events by System Organ Class and Preferred Term
- (11) Most Frequent Non-Serious Treatment-Emergent Adverse Events by System Organ Class and Preferred Term

The frequency distribution will be provided according to the rules below.

Number of subjects

- Summary tables other than (5), (6) and (9)
A subject with multiple occurrences of TEAE within a SOC will be counted only once in that SOC. A subject with multiple occurrences of TEAE within a PT will be counted only once in that PT.
Percentages will be based on the number of subjects in the safety analysis set.
- Summary tables for (5) and (6)
A subject with multiple occurrences of TEAE within a SOC or a PT will be counted only once for the TEAE with the maximum intensity.
Percentages will be based on the number of subjects in the safety analysis set.
- Summary table for (9)

A subject with a TEAE that occurs in more than one interval is counted in all the intervals that the TEAE occurs. For each time interval, a subject with multiple occurrences of TEAE within a SOC or a PT will be counted only once in that SOC or PT.

When calculating percentages for each time interval, the number of subjects at risk (i.e., subjects who either have an exposure or have an occurrence of TEAE, during or after the corresponding time interval) will be used as the denominator. The number of subjects whose onset of any one of the TEAEs is within the time interval will be used as the numerator.

- Summary table for (10)

Most frequent TEAEs refer to PTs whose percentages are at least 5.0% in any one of the treatment groups.

- Summary table for (11)

Most frequent Non-Serious TEAEs refer to PTs whose percentages are at least 5.0% in any one of the treatment groups. If no Non-Serious TEAEs exceed a frequency of 5.0%, the frequency cutoff of 2.0% will be used instead. Percentages will be based on the number of subjects in the safety analysis set.

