9.3.4 Follow-up

9.3.4.1 VISIT 7 (*Final visit of the Follow-up, 28 days after last dose*)

The Follow-up lasts for 4 weeks (28 days) from the day after the final dose of study drug. The following procedures should be performed at the final visit of the Follow-up (VISIT 7). If early termination occurs during the Treatment, the same procedures scheduled at VISIT 7 should be performed 4 weeks (28 days) after the end of treatment. If study termination occurs during the Follow-up, the same procedures scheduled at VISIT 7 should be performed.

- Pregnancy test (urine)
- Physical examination
- Vital signs and weight
- Status of menstruation recovery
- Clinical laboratory tests
- Pharmacodynamic measurements
- Standard 12-lead ECG
- AE
- Concomitant medications
- PGx sample collection (perform only in subjects who consent and from whom the sample has not been collected [see Section 9.1.12])

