10.2 Procedures

10.2.1 Collection and Reporting of AEs

10.2.1.1 AE Collection Period

Collection of AEs will commence from the time the subject signs the informed consent. Routine collection of AEs will continue until VISIT 7 (or early termination).

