13.1.5 Safety Analysis

The following analyses will be based on the safety analysis set.

(1) Secondary endpoint

Treatment-emergent adverse events

A TEAE is defined as an AE whose date of onset occurs on or after the start of study drugs for the Treatment.

TEAEs will be coded using the MedDRA dictionary. The frequency distribution will be provided using the system organ class (SOC) and the preferred term (PT) for each treatment group as follows:

- All TEAEs
- Drug-related TEAEs
- Intensity of TEAEs
- Intensity of drug-related TEAEs
- TEAEs leading to study drug discontinuation
- Serious TEAEs
- TEAEs over time

Laboratory test results, standard 12-lead ECGs, vital signs and weight

For continuous variables, the observed values and the changes from baseline will be summarized by treatment group for each visit using descriptive statistics. Case plots will also be presented for the observed values.

For categorical variables, shift tables showing the number of subjects in each category at baseline and each post-baseline visit will be provided for each treatment group.

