4.4.2 Dose Level and Regimen

At VISIT 3, subjects will be randomized in a 1:1 ratio to either the TAK-385 40 mg group or placebo group. Study drug (TAK-385 40 mg or TAK-385 placebo) will be administered from the day of VISIT 3 to the day before VISIT 6 (or until early termination) under double-blind conditions.

Figure 4 Schematic of Study Design

* In addition to Day -80~ -26, informed consent may be obtained before Day -80.

**VISIT 2 and 3: On days 1 to 5 of the menstrual cycle

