7.7 Study Drug Exposure and Compliance

Analysis Set: Safety Analysis Set

Analysis Duration of Exposure to Double- [1<= - <=14, 15<= - <=42,

Variable(s) : Blind Study Drug (days) 43<= - <=84, 85<= - <= Max]

Double-Blind Study Drug	[Min<= - <80, 80<= - <90, 90<= - <=Max]
Compliance (%)	<=Max]
Maximum Drug Holidays (days)	[0, 1<= - <4, 4<= - <=Max]

Analytical

Method(s) : (1) Study Drug Exposure and Compliance

Frequency distributions for categorical variables and descriptive statistics for continuous variables will be provided by treatment group and overall.

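### In the TEAEs-over-time table, off-drug subjects count as at risk only if they have a TEAE, so the Day 85+ percentages come out too high

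*SAP*

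**What the plan says.** SAP 7.11.1.2 plans a table (9) of TEAEs by SOC and PT over time, with onset categories "Time of Onset (day) [1<= - <=28, 29<= - <=56, 57<= - <=84, 85<= - <=Max". The denominator in each interval is "subjects who either have an exposure or have an occurrence of TEAE, during or after the corresponding time interval". The numerator is the number of subjects with a TEAE onset inside the interval. The counting rule just before it says: "A subject with a TEAE that occurs in more than one interval is counted in all the intervals that the TEAE occurs". The main TEAE tables in the same section use the safety analysis set as denominator.

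Five other places fix what this means for the last interval:

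- SAP 4.4.2: study drug "will be administered from the day of VISIT 3 to the day before VISIT 6 (or until early termination) under double-blind conditions". The heading of Protocol 9.3.3.1 places VISIT 6 on Day 85.
- SAP 7.1.1: the duration of exposure ends at the last double-blind dose.
- Protocol 13.1.5: "A TEAE is defined as an AE whose date of onset occurs on or after the start of study drugs for the Treatment". There is no upper limit after the last dose.
- Protocol 10.2.1.1: "Routine collection of AEs will continue until VISIT 7 (or early termination".
- Protocol 9.3.4.1: "The Follow-up lasts for 4 weeks (28 days) from the day after the final dose of study drug".

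SAP 7.7 ends its exposure categories with "43<= - <=84, 85<= - <= Max", so it allows for exposure beyond 84 days without saying how common that would be.

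**The concern.** A denominator should be settled by who was observed, not by who had the event. Under this rule, a subject on drug is at risk whatever happens to her. A subject off drug but still under AE collection is at risk only if she has a TEAE. Event-free observed subjects are removed, and subjects with events are kept in both numerator and denominator.

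The Day 85+ column is the only one for events starting after planned dosing ends. It could suggest a rise in adverse events after stopping that comes only from the denominator. It can also mislead between arms, because the percentage depends on how many subjects in each arm happened to be dosed on or after Day 85. The protocol names TEAEs over time as a planned safety display (13.1.5) and includes the Follow-up for safety assessment (6.2.1), so readers will look at this column.

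A second point is unclear: whether an occurrence in the denominator means onset or also covers an ongoing event. The numerator uses onset, but the counting rule speaks of every interval in which a TEAE occurs. This changes the size of the error, not its direction.

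**Working it through.** The plan gives no figure for this table, so there is none to reproduce.

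**Timing.** VISIT 6 is Day 85 and dosing stops the day before, so the last scheduled dose is Day 85 − 1 = Day 84. Follow-up of 28 days runs to Day 84 + 28 = Day 112. For an on-schedule completer, the whole Day 85+ interval is off drug and under AE collection.

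**Direction.** The numerator is the same under the SAP rule and under a rule based on observation. The SAP denominator cannot exceed the number observed. It is smaller as soon as one observed off-drug subject has no qualifying TEAE.

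**Size.** Assume 32 subjects per arm, all followed to VISIT 7, with events independent of late dosing. Let

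- e = subjects with TEAE onset from Day 85,
- o = other subjects with only an ongoing TEAE from Day 85 (0 if occurrence means onset),
- L = subjects whose last dose is on or after Day 85,
- k = subjects in the table row (k = e for any TEAE).

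Expected SAP denominator = L + (e + o)(32 − L)/32, and reported % = 100 k / denominator. An observation-based rule gives 100 k / 32.

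Example for e = 5, o = 0, L = 8: 8 + 5 × 24/32 = 11.75, and 5/11.75 = 42.6%.

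| Row | L = 0 | L = 8 | L = 16 | L = 24 | All observed |
|---|---|---|---|---|---|
| Any TEAE, e = 5, o = 0 | 100% | 42.6% | 27.0% | 19.8% | 15.6% |
| Any TEAE, e = 5, o = 5 | 50.0% | 32.3% | 23.8% | 18.9% | 15.6% |
| Any TEAE, e = 5, o = 10 | 33.3% | 26.0% | 21.3% | 18.0% | 15.6% |
| One PT, k = 2, e = 5, o = 0 | 40.0% | 17.0% | 10.8% | 7.9% | 6.3% |

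With e = 3 and o = 0, the any-TEAE row reads 100%, 29.3%, 17.1% and 12.1%, against 9.4%. The two rules agree when L = 32.

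**Between arms (o = 0).**

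- Equal events, e = 5 in each arm, with L = 4 in one and 12 in the other: 5/(4 + 4.375) = 59.7% against 5/(12 + 3.125) = 33.1%. Both should be 15.6%.
- Unequal events, 8 against 2 of 32 (25.0% against 6.3%): with L = 0 the row reads 100% against 100%. With 10% dosed late (L = 3.2 on average) it reads 8/10.4 = 76.9% against 2/5.0 = 40.0%. The difference of 18.8 points becomes 0 or 36.9.

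**Earlier intervals.** The same rule affects subjects who stop early and are still followed. With a 30% rate (9.6 of 32) and D such subjects, the result is 9.6/[(32 − D) + 0.3D]: 31.4% for D = 2 and 32.9% for D = 4. These are upper values, because the rule also admits off-drug subjects whose TEAE comes after the interval.

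**The case against.** The mechanism is hard to contest. The case on the other side is about size and weight.

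- **The Day 84 end of dosing.** The body of Protocol 9.3.3.1 puts VISIT 6 at 85 days after the initial dose. Under the day count in SAP 7.1.2 that is Day 86, so dosing to the day before would end on Day 85, inside the last interval. Every on-schedule completer would then be counted through exposure. This is a real inconsistency and should be reconciled. But the section heading says Day 85, SAP 7.1.3 schedules Week 12 on Day 85, the visits at Days 29, 57 and 85 are 28 days apart, and 12 weeks is 84 days. The weight of the documents is on Day 84.
- **Late dosing.** A later VISIT 6 moves subjects into the denominator. Supply would allow it (3 × 3 × 14 = 126 tablets, Protocol 8.1.1.2), and the Week 12 analysis window runs to Day 99. This stands: 100% is a limiting case, and at L = 24 the error is only 19.8% against 15.6%. The open top category in SAP 7.7 shows that late dosing is provided for, not how common it is.
- **The meaning of occurrence.** The category label and the numerator both refer to onset, so onset is the more natural reading. That is fair, but it is also the reading with the larger error.
- **Imbalance between arms.** Nothing in the documents suggests that late dosing would differ by arm, so the 4 against 12 contrast is only an illustration. The 8 against 2 example needs no such imbalance.
- **Weight.** This is one descriptive table with no test. That is true and limits the concern.

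The Handling Rules for Analysis Data were not available. SAP 7.11.1.2 states this denominator in full and does not refer to them for it.

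**Conclusion.** The concern holds. As written, the Day 85+ percentages in table (9) are too high under either reading of occurrence, unless every observed subject without a qualifying TEAE was dosed on Day 85 or later. The direction is certain under that condition. The size is not known, because the documents give neither the number dosed from Day 85 nor the number of late events. With 5 of 32 subjects affected and onset as the criterion, the row would read from 100% (nobody dosed late) down to 19.8% (24 dosed late), against 15.6%. These figures assume full follow-up to VISIT 7 and events independent of late dosing. Earlier intervals move by about 1 to 3 points at most in the cases examined. The table's counts, the summaries based on the safety analysis set and all efficacy results are unchanged. The rule should be corrected before the table is produced.

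**What to change.** In SAP 7.11.1.2, define the number at risk in an interval as the safety-set subjects whose AE collection period reaches that interval, whether or not they had a TEAE. Define the period as running from the first double-blind dose to VISIT 7, or to the end of AE collection if earlier, and exclude telephone contact made only to track the return of menstruation. Keep onset within the interval as the numerator, state that occurrence means onset, and bring the opening counting sentence into line. It is also useful, though not needed to correct the denominator, to show events with onset after the last dose separately. The heading and body text of Protocol 9.3.3.1 on the timing of VISIT 6 should be reconciled as well.

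The cost is one or two SAP sentences and a denominator reprogrammed from dates already collected. There are two small drawbacks: a subject observed for part of an interval counts in full, and some off-drug time enters the earlier columns. The separate display of post-treatment onset deals with the second.

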7.11.1.3 Displays of Pretreatment Events

Analysis Set: All Subjects Who Signed the Informed Consent Form

Analysis

Variable(s) : Pretreatment event (PTE)

Analytical : The following summaries will be provided using frequency distribution.

Method(s) : PTEs will be coded using the MedDRA and will be summarized using SOC and PT. SOC will be sorted alphabetically and PT will be sorted in decreasing frequency.

- (1) Pretreatment Events by System Organ Class and Preferred Term
- (2) Serious Pretreatment Events by System Organ Class and Preferred Term

The frequency distribution will be provided according to the rules below.

Number of subjects

A subject with multiple occurrences of PTE within a SOC will be counted only once in that SOC. A subject with multiple occurrences of PTE within a PT will be counted only once in that PT.

7.11.1.4 Displays of Run-in Adverse Events

Analysis Set: All Subjects Who Received Run-in Study Drug Analysis

Variable(s) : Run-in AE

Analytical The following summaries will be provided using frequency distribution.

Method(s) : Run-in AEs will be coded using the MedDRA and will be summarized using SOC and PT. SOC will be sorted alphabetically and PT will be sorted in decreasing frequency.

- (1) Run-in Adverse Events by System Organ Class and Preferred Term
- (2) Drug-Related Run-in Adverse Events by System Organ Class and Preferred Term
- (3) Serious Run-in Adverse Events by System Organ Class and Preferred Term

The frequency distribution will be provided according to the rules below.

Number of subjects

A subject with multiple occurrences of run-in AE within a SOC will be counted only once in that SOC. A subject with multiple occurrences of run-in AE within a PT will be counted only once in that PT.

7.11.2 Clinical Laboratory Evaluations

7.11.2.1 Hematology and Serum Chemistry

Analysis Set: Safety Analysis Set

Analysis

Variable(s) : Hematology

RBC

WBC

WBC Differentials (Neutrophils, Eosinophils, Basophils, Lymphocytes, Monocytes)

HGB

Hematocrit (HCT)

Platelets

CONFIDENTIAL

Serum Chemistry

ALT	AST	Lactate dehydrogenase (LDH)
Gamma glutamyl transferase (GGT)	Albumin	Alkaline phosphatase (ALP)
Bilirubin (Total bilirubin)	Protein (Total protein)	Cholesterol (Total cholesterol)
High density lipoprotein (HDL) cholesterol	Low density lipoprotein (LDL) cholesterol	Triglycerides
Glucose	HGB A1C	Creatinine
Blood urea nitrogen (BUN)	Creatine kinase	Urate
Sodium	Potassium	Chloride
Calcium	Phosphate	Magnesium

Visit: Baseline , Week 4, 8, 12 and Follow-up

Analytical

Method(s) : For each variable, summaries (1) to (3) will be provided by treatment group.

For applicable variables, summaries (4) and (5) will be provided by treatment group.

(1) Summary of Laboratory Test Results and Change from Baseline by Visit

Descriptive statistics for observed values for each visit and changes from baseline will be provided.

(2) Case Plots

Plots over time for each subject will be presented.

(3) Summary of Shifts of Laboratory Test Results

Shift tables showing the number of subjects in each category at baseline and each post-baseline visit will be provided.

For each laboratory test, the laboratory values will be classified as "Low", "Normal" or "High" relative to the normal reference range provided by the central laboratory. The shift tables will be based on

these classifications.

(4) Number and Percentage of Subjects with Markedly Abnormal Values of Laboratory Parameters

Overall frequency distributions of MAV during treatment period will be provided. If a laboratory parameter has both lower and upper MAV criteria, analysis will be performed for each. Further details are given in Appendix.

(5) Number and Percentage of Subjects with Elevated Liver Enzyme Laboratory Parameters

Overall frequency distributions of elevated hepatic parameters during treatment period will be provided. Further details are given in Appendix.

7.11.2.2 Urinalysis

Analysis Set: Safety Analysis Set

Analysis

Variable(s) : Protein [-, +-, 1+, 2+, 3+, 4+]

Glucose [-, 1+, 2+, 3+, 4+, 5+]

Occult blood [-, +-, 1+, 2+, 3+]

Bilirubin [-, +-, 1+, 2+, 3+]

Urobilinogen [+-, 1+, 2+, 3+]

Visit: Baseline, Week 4, 8, 12 and Follow-up

Analytical

Method(s) : For each variable, summaries (1) and (2) will be provided by treatment group.

(1) Number of Subjects in Categories of Urine Laboratory Test Results

Shift tables showing the number of subjects in each category at baseline and each post-baseline visit will be provided.

(2) Summary of Shifts of Urine Laboratory Test Results

Shift tables showing the number of subjects in each category at baseline and each post-baseline visit will be provided.

For each urine laboratory test, the laboratory values will be

classified as "Normal" or "Abnormal " relative to the normal reference range provided by the central laboratory. The shift tables will be based on these classifications.

7.11.3 Vital Signs

7.11.3.1 Vital Signs and Weight

Analysis Set: Safety Analysis Set

Analysis

Variable(s) : Systolic Blood Pressure
Diastolic Blood Pressure
Pulse Rate
Body temperature
Weight

Visit: Baseline, Week 4, 8, 12 and Follow-up

Analytical

Method(s) : For each variable, summaries (1) and (2) will be provided by treatment group.
For applicable variables, summaries (3) will be provided by treatment group.
(1) Summary of Vital Signs Parameters and Weight and Change from Baseline by Visit
Descriptive statistics for observed values for each visit and changes from baseline will be provided.
(2) Case Plots
Plots over time for each subject will be presented.
(3) Number and Percentage of Subjects with Markedly Abnormal Values of Vital Signs Parameters
Overall frequency distributions of MAV during treatment period will be provided. If a vital sign parameter has both lower and upper MAV criteria, analysis will be performed for each. Further details are given in Appendix.

7.11.4 12-Lead ECGs

7.11.4.1 12-lead ECG

Analysis Set: Safety Analysis Set

Analysis

Variable(s) : 12-Lead ECG Interpretation [Within Normal Limits, Abnormal but not Clinically Significant, Abnormal and Clinically Significant]

Visit: Baseline , Week12 and Follow-up

Analytical

Method(s) : For 12-lead ECG interpretation, summary (1) will be provided by treatment group.

(1) Summary of Shift of 12-lead ECG Interpretation

Shift table showing the number of subjects in each category at baseline and each post-baseline visit will be provided.

7.11.5 Other Observations Related to Safety

7.11.5.1 Return of Menstrual Cycles

Analysis Set: Safety Analysis Set

Analysis

Variable(s) : Duration of Menstruation Recovery (Days)

Analytical

Method(s) : Summary (1) will be provided by treatment group.

(1) Summary of Duration of Menstruation Recovery

Descriptive statistics for observed values will be provided.

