9.1.18 Status of Menstruation Recovery

If the first menstruation after the end of study drug administration is observed before the VISIT 7 in the Follow-up, the date of onset of the first menstruation is recorded in the eCRF. If menstruation recovery is not observed by the VISIT 7 in the Follow-up, follow-up will be continued as far as possible through telephone calls or other means until the recovery of the first menstruation. If menstruation recovery is observed during continued follow-up, the date of recovery should be recorded in the eCRF. The status at the end of menstruation follow-up will be recorded in the eCRF regarding menstruation recovery. After the Follow-up, follow-up will not be continued in subjects who undergo surgery or receive hormone therapy for the treatment of uterine fibroids before the recovery of menstruation.

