7.0 METHODS OF ANALYSIS AND PRESENTATION

7.1 General Principles

All statistical analyses will be conducted using SAS® Version 9.2, or higher.

A statistical test for the primary endpoint will be reported as 2-sided and will be assessed at $\alpha=0.05$ significance level and all confidence intervals will be reported as 2-sided unless otherwise stated. P-values will be rounded to 4 decimal places prior to assessment of statistical significance.

Means and medians will be presented to 1 more decimal place than the recorded data. The standard deviations (SDs) will be presented to 2 more decimal places than the recorded data. Confidence intervals about a parameter estimate will be presented using the same number of decimal places as the parameter estimate.

Where appropriate, variables will be summarized descriptively by study visit. For the categorical variables, the count and proportions of each possible value will be tabulated by treatment group. The denominator for the proportion will be based on the number of subjects who provided non-missing responses to the categorical variable. For continuous variables, the number of subjects with non-missing values, mean, median, SD, minimum, and maximum values will be tabulated. Confidence intervals for continuous variables will be calculated based on t-statistics and ones for categorical variables will be based on Wald confidence intervals without using any model, unless otherwise stated.

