Mean NRS score from Day 1 to earlier of Day 28 or Follow-up Day 3.

Similarly, Mean NRS score from Day 29 to 56 and from Day 57 to 84 will be defined as mean NRS score from Day 29 to earlier of Day 56 or Follow-up Day 3 and from Day 57 to earlier of Day 84 or Follow-up Day 3, respectively.

Number of days without pain symptoms (NRS = 0) from Day 1 to 28, 29 to 56, and 57 to 84

((number of days without pain symptoms (NRS = 0) from Day 1 to earlier of Day 28 or Follow-up Day 3)/(number of days with available data from Day 1 to earlier of Day 28 or Follow-up Day 3))*100 (rounded to 1 decimal places)

Number of days without pain symptoms (NRS = 0) from Day 29 to 56 and from Day 57 to 84 will be derived in a similar manner.

Use of analgesic medications during the 28 days before the final dose of study drug

((number of days with analgesic medications use during the last 28 days of the treatment)/(number of days with available data during the last 28 days of the treatment))*100 (rounded to 1 decimal places)

Myoma volumes

$$D1*D2*D3*\pi/6 \text{ (cm}^3\text{)}$$

Definitions of D1, D2 and D3 are shown in protocol.

Uterine volumes will be similarly calculated.

Duration of Menstruation Recovery

Date of menstruation recovery - date of last dose of double-blind study drug

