7.1.4 Methods for Handling Missing Data

All available efficacy and safety data will be included in data listing and tabulations. No imputation of values for missing data will be performed unless otherwise specified.

- For UFS-QoL, published scoring manuals and guidelines will be used to calculate UFS-QoL and handle missing data (see Appendix 3).
- For myoma or uterus volume, if D1 and D2 of the myoma or uterus are present but D3 is missing, then the volume will be calculated as $D1*D2*D2*\pi/6$ (cm^3).
- For LH, FSH, E₂, P and clinical laboratory tests, values less than the lower limit of quantification will be treated as zero when calculating the descriptive statistics.

- Disease duration with first diagnosis date of uterine fibroid that are completely or partially missing will be derived as follows:
 1. If the year is missing, then the disease duration will be treated as missing.
 2. If the year is present but the month is missing, then the month will be treated as January for the calculation.

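### SAP 7.11.5.1 summarises time to menstruation recovery only in subjects with a recovery date and plans no count of those who end follow-up unrecovered

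*SAP*

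**What the plan says.** SAP 7.1.1 defines the duration of menstruation recovery as "Date of menstruation recovery - date of last dose of double-blind study drug". SAP 7.11.5.1 gives it one output, by treatment group in the safety analysis set: "Descriptive statistics for observed values will be provided". Three general rules fill in the detail.

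- SAP 7.1: "For continuous variables, the number of subjects with non-missing values, mean, median, SD, minimum, and maximum values will be tabulated".
- SAP 7.1.4 on missing values: "No imputation of values for missing data will be performed unless otherwise specified". No exception is made for this variable.
- SAP 7.1.4 on reporting: "All available efficacy and safety data will be included in data listing and tabulations".

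The SAP text has no censoring rule, no time-to-event estimate and no count of subjects recovered or not recovered.

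Protocol 9.1.18 governs collection. If menstruation has not returned by VISIT 7, "follow-up will be continued as far as possible through telephone calls or other means until the recovery of the first menstruation". One exception applies once the Follow-up is over: "follow-up will not be continued in subjects who undergo surgery or receive hormone therapy for the treatment of uterine fibroids before the recovery of menstruation". The section also states: "The status at the end of menstruation follow-up will be recorded in the eCRF regarding menstruation recovery". Protocol 6.2.1 names recovery of menstruation as part of the safety purpose of the Follow-up.

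**The concern.** The protocol foresees subjects whose contact ends before menstruation returns, but the analysis has no place for them. Without a recovery date there is no duration, and without imputation there is no contribution to the mean or median.

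The loss is not neutral for completers. Protocol 7.3.1.1 and 7.3.3 prohibit sex hormone preparations and fibroid surgery until VISIT 7, which Protocol 9.3.4.1 places 28 days after the last dose. A completer stopped by the surgery or hormone rule is therefore known to have a recovery time beyond about Day 28. Dropping her discards that information.

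The two arms are exposed differently. Placebo subjects who keep the 25 to 38 day cycles required at entry will mostly menstruate before VISIT 7. Subjects on a drug that induces amenorrhea (Protocol 4.1) are more likely to reach VISIT 7 unrecovered. At stake is whether the only planned summary of recovery describes the active arm fairly.

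**Working it through.** The documents contain no figure on recovery to reproduce: no recovery times, no expected number unrecovered and no rate of later surgery or hormone therapy. What follows is an illustration. Only the 28 days, the 25 to 38 day cycles, the 84 dosing days and the 32 per group come from the documents.

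**Model for the active arm (assumed).** Recovery time T is lognormal with median 36 days and log-SD 0.3.
- Mean: 36 × exp(0.3²/2) = 37.7 days.
- SD: 37.7 × √(exp(0.3²) − 1) = 11.6 days.
- Standard error of one arm's mean: 11.6/√32 = 2.0 days.

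Stopping starts at Day 28 with constant hazard r, so a subject with recovery time t is still followed at t with probability S(t) = exp(−r × max(t − 28, 0)). The stopped share is 1 − E[S(T)], and the observed-only mean is E[T·S(T)]/E[S(T)].

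| Stopped | About how many of 32 | r per day | Observed-only mean short by | Observed-only median short by | Kaplan-Meier median, true stop dates | Kaplan-Meier median, censored at VISIT 7 |
|---|---|---|---|---|---|---|
| 2% | 1 | 0.0019 | 0.23 days | 0.21 days | 36.0 | 35.86 |
| 5% | 2 | 0.0050 | 0.58 days | 0.53 days | 36.0 | 35.65 |
| 10% | 3 | 0.0106 | 1.19 days | 1.08 days | 36.0 | 35.27 |

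**Range of assumptions at 10% stopped** (medians 30, 36 and 45 days, each with log-SD 0.2, 0.3 and 0.4):
- Random stopping: mean 0.50 to 1.96 days short, median 0.49 to 1.60 days short. The mean shortfall is below one standard error of the arm's mean in all nine combinations; the largest is 1.96 against 2.4. The Kaplan-Meier median is unbiased with true stop dates and 0.28 to 1.29 days short if stops are censored at VISIT 7.
- Slow recoverers stop more (hazard 2r if T exceeds 42 days, 0.5r otherwise): mean 0.71 to 2.40 days short, at most about one standard error. Kaplan-Meier median 0.01 to 0.29 days short.
- Only subjects with T of 42 days or less can stop: the mean shortfall runs from −1.29 to +0.53 days, so the sign can reverse. The Kaplan-Meier median is 0.01 to 2.91 days too long.
- 10% lost for reasons unrelated to recovery, soon after the last dose: no change in the mean.

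The 42-day split is only a device for making stopping depend on recovery time.

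**Placebo arm (assumed).** With cycle length uniform over 25 to 38 days, VISIT 3 on menses day 1 to 5 and the last dose on Day 84, recovery falls on Day 1 to 31 after the last dose, with mean 17.1 and 5.7% beyond Day 28. With random cycle phase instead, the mean is 15.7 and 11.2% fall beyond Day 28. At the 10% hazard above (0.0106), 0.1% to 0.4% of placebo subjects are stopped and the mean is 0.01 to 0.07 days short. A reader comparing the two group means would see a difference too small by 1.19 − 0.07 = 1.1 to 1.19 − 0.01 = 1.2 days.

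**The case against.** The best case for the plan has five parts.

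- **Follow-up is meant to run to recovery.** Protocol 6.1.1, 9.1.18 and 9.3.5 all seek a date for every subject, so few may be missing. With a 2% chance of stopping, the probability that none of 32 stops is 0.98³² = 52%. This stands, and the bias is then zero.
- **The gap is visible.** The number with values is tabulated, the size of the safety analysis set is tabulated by group (SAP 7.3.7), and available data are listed. This stands in part. The difference between the two counts mixes subjects known to be unrecovered, subjects stopped for treatment and subjects lost to contact, and it corrects neither the mean nor the median.
- **The effect is small and the variable is not an endpoint.** Both are true. SAP 7.11.5.1 plans no test and no between-group comparison.
- **Kaplan-Meier is not always better.** In the scenario where only faster recoverers stop, its median is further from the truth than the observed-only median in five of the nine combinations. Its censoring dates may also be missing: Protocol 9.1.18 mentions no last-contact date, and Protocol 9.1.6 asks about medication only through VISIT 7. This rules out replacing the observed statistics.
- **The Handling Rules for Analysis Data may deal with it.** That document was not available, and the SAP does not cite it for this variable.

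Two stronger readings are tempting. A reader might infer that the table necessarily understates time to recovery. The documents do not say who has surgery or starts hormone therapy after VISIT 7, so the direction is conditional. A reader might also suppose that the missing subjects are simply the slowest. Removing the slowest 3 to 8 of 32 from assumed lognormal times lowers the mean by roughly 2 to 12 days, but nothing in Protocol 9.1.18 selects subjects in that way.

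**Conclusion.** The point holds as a minor one. The planned mean and median treat censored recovery times as if they did not exist, and the section plans no count by recovery status.

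For completers stopped by the surgery or hormone rule, the mean and median are too short if stopping is unrelated to recovery time or commoner in slow recoverers. This falls mainly on the active arm. The sign can reverse if faster recoverers stop. Subjects who terminate early may start such treatment sooner, so the Day 28 argument does not cover them.

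The true size is unknown. With 10% stopped at random and the assumed lognormal times, the mean is about 0.5 to 2.0 days short, less than one standard error of an arm's mean. Confidence is medium because every recovery and stopping input is assumed. The primary test and the listed endpoints are not affected.

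**What to change.** Amend SAP 7.11.5.1 in two steps.

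1. Add, by treatment group, the number and percentage of the safety analysis set recovered, not recovered at the end of follow-up, and unknown, with the reason where recorded. The end-of-follow-up status is already on the eCRF, so the counts need no new data.
2. Keep the observed-value statistics, labelled as applying only to subjects with a recovery date. Alongside them, give a Kaplan-Meier median with 95% confidence interval and the proportion recovered by Follow-up Day 28, by treatment group. Censor unrecovered subjects at the last date documented as not recovered, or at VISIT 7 if no later date is captured. State that this assumes non-informative censoring.

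The cost is a little SAP wording and one standard procedure, plus a check of which censoring dates exist. If only VISIT 7 dates exist, the correction is partial: in the base case at 10% stopped, the Kaplan-Meier median is 36.0 − 35.27 = 0.7 days short, against 1.1 for the observed-only median. The counts in step 1 then carry most of the information. The Kaplan-Meier estimate is itself biased if stopping depends on recovery time, so it should be read beside those counts.
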